Product Name	Products Used within the FIRE AND ICE Trial: Arctic Front® & Arctic Front Advance® Cardiac CryoAblation Catheter System (Cryo Arm; Manufacturer Medtronic, Inc; model number 2AF233 and 2AF283) and NaviStar® ThermoCool® Ablation Catheter (Radiofrequency Arm; Manufacturer Biosense Webster, Inc.)
Sponsor	Medtronic International Trading Sàrl [name]
Indication under investigation	The proposed indication for the Arctic Front Advance® Cardiac CryoAblation Catheter System is as follows: The Arctic Front Advance® Cardiac CryoAblation Catheters are indicated for the treatment of drug refractory recurrent symptomatic paroxysmal and persistent atrial fibrillation (AF). The proposed indications are within the approved indications in Europe for all involved catheter systems.
Investigation Purpose	The FIRE AND ICE Trial collected data to compare efficacy and safety of isolation of the pulmonary veins (PV) using a Cryoballoon catheter versus a radiofrequency ablation with a ThermoCool catheter in patients with drug refractory symptomatic paroxysmal atrial fibrillation (AF). The purpose of this retrospective data collection on re-ablations performed in both treatment arms (Cryo arm and Radiofrequency arm) of the FIRE AND ICE Trial is to gain insight into re-occurrence of atrial arrhythmias resulting in a re-ablation after a performed index ablation procedure. Data to be collected from subject charts include pulmonary vein anatomy, documented atrial arrhythmias prior to re-ablation, pulmonary vein reconnection, pulmonary vein ablation lesion gaps and gap location, ablation lesions performed during the re-ablation, procedure parameters of the RF or cryo catheter utilized during the re-ablation, and success of re-ablations performed. The resulting data may provide insight into the possible causes for re-occurrence of atrial arrhythmias requiring re-ablation.
Product Status	Retrospective Data Collection only on re-ablations performed within

Medtronic Confidential

FIRE AND ICE – Re-Ablations (retrospective data collection)

Clinical Investigation Plan

Version 1.0, 20 Sep 2017

Page 9 of 46

Medtronic

the FIRE AND ICE Trial (marked products).	
Objective(s) and Endpoints	
• Summarize the documented atrial arrhythmias prior to re-ablation• Summarize the number of reconnected pulmonary veins• Summarize the number of gaps and location of gaps present in pulmonary vein ablation lesions• Summarize ablation lesion sets created during re-ablation procedure• Summarize acute procedural success of re-ablation procedure• Summarize re-ablation procedure times.• Summarize the length of stay during the hospitalization for re-ablation• Summarize the anti-arrhythmic drug use at time of discharge from the re-ablation procedure.• Summarize adenosine testing
Study Design	Retrospective Data Collection on re-ablations performed within the FIRE AND ICE Trial. No change in the subject population or participating sites. It is estimated to collect the additional retrospective data on re-ablations within 2 months.
Randomization	Not applicable.
Sample Size	No new subjects will be enrolled. In total 119 re-ablations were performed in the FIRE AND ICE Trial. These applicable subjects will be now asked for their consent for the additional data collection on re-ablation procedures.
Inclusion/Exclusion Criteria	Not applicable.
Study Procedures and Assessments	Not applicable. Only data of already performed procedures will be collected.
Safety Assessments	Not applicable. Safety reporting on all events was already performed as part of the FIRE AND ICE Trial.
Statistics	A total of 119 repeat ablations were reported in 110 subjects in the FIRE AND ICE trial. The primary analysis cohort for this CIP will be subjects that provide informed consent for a retrospective data collection (if required by local law / EC). One final analysis will be completed. Data from all consented subjects will be entered into the project database. At the completion of the review by the endpoint review committee, the endpoint review committee classifications will be entered into the database and the database will be frozen. Nine objectives are defined for this CIP as listed above.

Medtronic Confidential

4. Introduction

4.1. Background

The FIRE AND ICE Trial was a controlled, prospective, non-inferiority, parallel-group, randomized, interventional, open, blinded outcome assessment (PROBE-Design), multi-centre trial, comparing efficacy and safety of isolation of the pulmonary veins with a Cryoballoon catheter versus a Radiofrequency ablation with a ThermoCool® catheter in subjects with paroxysmal atrial fibrillation¹.

A total of 762 subjects underwent randomization within the FIRE AND ICE Trial: 378 assigned to cryoballoon ablation and 384 assigned to radiofrequency ablation. The mean duration of follow-up was 1.5 years. The primary efficacy endpoint (time to first documented recurrent atrial arrhythmia defined as AF>30s, AT or AFL, AAD prescription or repeat ablation) was reached in 138 subjects in the cryoballoon group and in 143 in the radiofrequency group and the related data published in the New England Journal of Medicine on April 4, 2016². The primary efficacy endpoint was observed to occur at similar rate in the cryoballoon and radiofrequency arms (1-year Kaplan–Meier event rate estimates, 34.6% and 35.9%, respectively; hazard ratio, 0.96; 95% confidence interval [CI], 0.76 to 1.22; P<0.001 for noninferiority). The secondary analyses on reintervention and rehospitalization showed that subjects treated with cryoballoon as opposed to radiofrequency current (RFC) ablation had significantly fewer repeat ablations (11.8% cryoballoon vs. 17.6% RFC; p=0.03), direct-current cardioversions (3.2% cryoballoon vs. 6.4% RFC; p=0.04), all-cause hospitalizations (32.6% cryoballoon vs. 41.5% RFC; p=0.01), and cardiovascular rehospitalizations (23.8% cryoballoon vs. 35.9% RFC; P=0.01) during follow-up. Additionally, both subject groups (Cryo and RF arm) improved in quality-of-life scores after AF ablation³.

After the first ablation procedure, in total 119 re-ablations at 15 sites were performed, thereof 49 in the Cryo arm and 70 in the RF arm. The frequency of re-ablation procedures and energy modality of catheter used during the re-ablation was collected during the FIRE AND ICE Trial, but limited data surrounding the re-ablation procedures were collected.

4.2. Purpose

The purpose of this retrospective data collection on re-ablations performed in both treatment arms (Cryo arm and Radiofrequency arm) of the FIRE AND ICE Trial is to gain insight into re-occurrence of atrial arrhythmias resulting in a re-ablation after a performed index ablation procedure. Data to be collected from subject charts include pulmonary vein anatomy, documented atrial arrhythmias prior to re-ablation, pulmonary vein reconnection, pulmonary vein ablation lesion gaps and gap location, ablation lesions performed during the re-ablation, procedure parameters of the RF or cryo catheter utilized during the re-ablation, and success of re-ablations performed. The resulting data may provide insight into the possible causes for re-occurrence of atrial arrhythmias requiring re-ablation.

5. Data to be collected

Administrative Information

- Data Release Form process
- Subject status
- Randomization group assigned within FIRE AND ICE including date of index ablation

Additional data on index ablation

- Data on non-pulmonary vein lesions made
- Cryo Arm (per PV): number of freezes, minimum temperature, duration per freeze, time to effect of freeze, bonus freeze and freeze duration / bonus freeze based on TTE
- RF Arm (per PV): power (watt) minimum, power (watt) maximum, smart touch force measurements (g) minimum, smart touch force measurements (g) maximum and complete RF time (for one side)

Subject characteristics at time of re-ablation and indication for re-ablation

- Date of hospital admission for re-ablation
- Indication for repeat ablation (including symptoms and way of arrhythmia recurrence documentation)
- PV anatomy / stenosis
- Recovered conduction gaps, including localization of gaps and differentiation of gaps (spot gap or linear gap)
- Vein isolation summary pre-ablation / results of PV mapping
- Ablation strategy on PVs chronically isolated
- Membrane-active AADs at time of re-ablation and at discharge after re-ablation
- Anticoagulation at time of re-ablation
- Adenosine use

Procedure parameters

- Rhythm at start of procedure ECG
- Catheters used to perform lesions / energy source used for re-ablation
- Visualization / navigational tools used
- Methods for determining balloon occlusion (Cryo)
- Phrenic nerve monitoring (Cryo Arm)
- Ablation lesions performed
- Cryo Arm (per PV): number of freezes, minimum temperature, duration per freeze, time to effect of freeze and bonus freeze
- RF Arm (per PV): power (watt) minimum, power (watt) maximum, smart touch force measurements (g) minimum, smart touch force measurements (g) maximum and complete RF time (for one side)
- Other lesion sets beyond PVI

Procedure times & procedure summary

- Total procedure times
- Fluoroscopy times and dosage
- LA dwell time
- 3D mapping time
- ACT time (lowest / highest)
- Sedation type
- Cryo Arm: only Arctic Front Advance catheters used / duration of freezes less than planned
- Phrenic nerve injury
- Cardioversion during procedure

Results of re-ablation & discharge

- Success / all targeted PVs isolated / outcome other lesion sets beyond PVI
- Rhythm(s) at end of procedure
- Date of discharge and discharge status (including prolonged hospitalization)
- Re-occurrence of arrhythmia during hospital stay
- Cardioversion after re-ablation due to early AT/AF recurrence
- Membrane-active AADs at time of discharge

6. Objectives and Endpoints

6.1. Objectives and Endpoints

Rationale for study endpoints

Study endpoints have been chosen based on the 2012 HRS/EHRA/ECAS Expert Consensus Statement on Catheter and Surgical Ablation of Atrial Fibrillation⁴. Definitions, mechanisms, and treatment strategies for atrial arrhythmias are outlined in the expert consensus statement. The objectives and endpoints of this data collection reflect these definitions, mechanisms, and treatment strategies. Hospitalization may be the result of a procedural complication, and therefore has been included as an endpoint in this CIP.

6.1.1. Objective: Atrial arrhythmias prior to re-ablation

Summarize the documented atrial arrhythmias prior to re-ablation

Endpoint: Each documented atrial arrhythmia will be classified into one of the following categories:

- Atrial Fibrillation
 - Paroxysmal
 - Persistent
- Atrial Tachycardia
- Atrial Flutter
 - Typical
 - Atypical

6.1.2. Objective: Reconnected pulmonary veins

Summarize the number of reconnected pulmonary veins

Endpoint: Each pulmonary vein will be classified as electrically isolated or not prior to re-ablation. Electrically isolated is defined as bi-directional block, entrance and exit block of PV potentials.

6.1.3. Objective: Number and location of gaps in pulmonary vein ablation lesions

Summarize the number of gaps and location of gaps present in pulmonary vein ablation lesions

[figure not shown]
Endpoint: For a redo conducted with a focal catheter and 3D EA mapping, a gap within the pulmonary vein ablation lesion is defined as an electrically reconnected pulmonary vein which after a single spot re-ablation the response to re-ablation is either PV re-isolation or PV activation-sequence change. Ongoing PV conduction after a single spot re-ablation is attributed to an additional gap. Additional gaps are defined similarly.

For a redo conducted with no 3D EA Mapping, gap location may have been estimated utilizing a mapping catheter.

Each gap location will be identified by the classifications provided in Error! Not a valid bookmark self-reference.. To define the location of a gap, including the differentiation for spot gap or linear gap the ipsilateral LA-PV junction is divided into 6 equally distributed segments; superior, antero-superior, antero-inferior, inferior, postero-inferior, and postero-superior.

Spot gap is defined as millimeter size, requiring only a single application without moving the catheter. Linear gap (larger continuous gap) is defined by requiring multiple applications or drawing of the catheter.

Figure 1: Pulmonary Vein Gap Locations

6.1.4. Objective: Ablation lesion sets performed

Summarize ablation lesion sets created during re-ablation procedure.

Endpoint: Each lesion set during re-ablation will be classified into one of the following categories:

- Pulmonary vein isolation (PVI)
- LA AF Trigger
- RA AF Trigger
- Superior vena cava trigger
- Inferior vena cava trigger
- Cavotricuspid Isthmus (CTI)
- Mitral valve isthmus or line
- Left sided roofline
- Complex fractionated atrial electrogram (CFAE)
- Posterior wall
- AVNRT ablation
- other

6.1.5. Objective: Acute procedural success

Summarize acute procedural success as assessed by the sites

Endpoint: Definition of success for each lesion set found below

- Pulmonary vein isolation (PVI)
 - Acute failure is defined as inability to isolate the pulmonary vein (minimally assessed for entrance block and, where assessable, exit block). Acute success is defined as the absence of acute failure.
- LA AF Trigger
 - Acute success is defined as elimination of trigger by ablation procedure.
- RA AF Trigger
 - Acute success is defined as elimination of trigger by ablation procedure.
- Superior vena cava trigger
 - Acute success is defined as elimination of trigger by ablation procedure.
- Inferior vena cava trigger
 - Acute success is defined as elimination of trigger by ablation procedure.
- Cavotricuspid Isthmus (CTI)

- Acute success is defined as bidirectional conduction block at the CTI line
- Mitral valve isthmus ablation
 - Acute success is defined as bidirectional conduction block at the mitral isthmus line
- Left atrial roofline
 - Acute success is defined as confirmed block at the roof line
- Left atrial posterior wall
 - Acute success is defined as confirmed block at the posterior wall
- Complex fractionated atrial electrogram (CFAE)
 - Acute success is defined when ablation of electrograms resulted in termination of atrial fibrillation to sinus rhythm or until all complex fractionated regions were completely eliminated
- AVNRT ablation
 - Acute success is defined as 1) no AVNRT inducibility; 2) no jump; 3) single echo only.
- Other

6.1.6. Objective: Re-ablation procedure times

Summarize re-ablation procedure times.

Endpoint:

1. *Total procedure time* is defined as time from first venous access to time of last sheath removal.
2. *Left atrial dwell time* is defined as time from transseptal puncture to time of removal of last sheath from the left atrium.
3. *Fluoroscopy time* is defined as total fluoroscopy time used during the procedure.

6.1.7. Objective: Re-ablation hospitalization length of stay

Summarize the length of stay during the hospitalization for re-ablation

Endpoint: Length of stay is defined as the number of days from admission to discharge.

6.1.8. Objective: Anti-arrhythmic drug use at re-ablation hospitalization discharge

Summarize the anti-arrhythmic drug use at time of discharge from the re-ablation procedure.

Endpoint: Anti-arrhythmic drug is defined as a Class I or III antiarrhythmic drug

6.1.9. Objective: Summarize adenosine testing

Summarize adenosine testing

Endpoint: Adenosine testing utilized at the time of re-ablation.

7. Study Design

Additional retrospective data collection on data of the performed re-ablations (procedural data) within the FIRE AND ICE Trial in both treatment arms.

The FIRE AND ICE Trial was an investigator initiated, controlled, prospective, non-inferiority, parallel-group, randomized, interventional, open, blinded outcome assessment (PROBE-Design), multi-center trial, comparing efficacy and safety of isolation of the pulmonary veins with a Cryoballoon catheter versus a Radiofrequency ablation with a ThermoCool® catheter in subjects with paroxysmal atrial fibrillation²¹.

7.1. Duration

The duration of the data collection for this project is expected to be 2 months, from initiation of first site, data collection, and closing of final site. No subject follow-up is required as the project is retrospective data collection only.

7.2. Rationale

Additional procedural re-ablation data will be collected retrospectively of all enrolled FIRE AND ICE subjects who had a re-ablation procedure during the follow-up period.

Within the FIRE AND ICE Trial, the occurrence of a re-ablation procedure, and the energy modality utilized during the procedure (Cryo or RF) were documented, but limited details on the performed re-ablation procedure were captured. Having additional data surrounding the re-ablation procedures may provide insight into the re-occurrence of atrial arrhythmias resulting in a re-ablation procedure.

8. Product Description (N/A)

Retrospective data collection only. No new assessments will be made nor any products used within this project.

9. Selection of Subjects

9.1. Study Population

No new subjects will be enrolled. Subject population enrolled in the related FIRE AND ICE Trial had drug refractory symptomatic paroxysmal atrial fibrillation with at least two episodes in the last three months prior to the trial enrollment and at least one episode documented. In addition, documented treatment

failure of at least one AAD Type I or III, excluding beta-blocker and AAD intolerance and an age range between 18 and 75 years.

9.2. Subject Enrollment (N/A)

Retrospective data collection only. No new subjects will be enrolled under this CIP.

Prior to any entry of retrospective subject data into the project database, the subject has to sign and date the Data Release Form. A subject is considered as “active subject” within this project at the time the Data Release Form has been fully signed and dated.

The medical files (subject records) at the participating site should indicate that the subject is an active subject within the retrospective data collection.

9.3. Inclusion Criteria (N/A)

No new subjects will be enrolled under this CIP. All subjects of whom the additional re-ablation data will be collected are enrollment and valid subjects within the FIRE AND ICE Trial.

9.4. Exclusion Criteria (N/A)

Not applicable. All subjects of whom the additional re-ablation data will be collected are enrollment and valid subjects within the FIRE AND ICE Trial.

10. Study Procedures

No study procedures will be performed under this CIP. Retrospective data will be collected on performed re-ablations occurred during the FIRE AND ICE follow-up period.

10.1. Schedule of Events (N/A)

Retrospective data collection only. Data on performed re-ablation procedures will be collected that were performed during the follow-up period of the FIRE AND ICE Trial.

10.2. Subject Screening (N/A)

No applicable – no new subjects will be screened or enrolled under this CIP.

10.3. Prior and Concomitant Medications (N/A)

Not applicable as retrospective data collection only.

10.4. Subject Consent (Data Release Form)

A signed and personally dated by the investigator or authorized designee and subject, sponsor and ethics committee (EC) / institutional review board (IRB) approved data release form, written in accordance with the country-specific applicable data privacy acts and the Data Protection Directive (95/46/EC), will be obtained from every subject who had a re-ablation procedure within the FIRE AND ICE Trial prior to the collection of any additional data (if required). Ethical principles as laid down by the Declaration of Helsinki (18th World Medical Assembly, Helsinki 1964) and all applicable amendments laid down by the World Medical Assemblies have been considered for the data release form as well as for the subject consenting process.

The process of obtaining subject data release form by the principal investigator or his/her authorized designee shall:

- Not waive or appear to waive subject's legal rights
- Use language that is non-technical and understandable to the subject
- Provide ample time for the subject to read and understand the data release form and to ask questions, receive answers and consider participation
- Avoid any coercion or undue improper influence on, or inducement of, the subject to participate in the project

The sponsor should avoid improper influence on, or inducement of, the subject, monitor, any investigator(s) or other parties participating in, or contributing to, the retrospective data collection project.

For deceased subjects, in accordance with the country-specific data privacy acts and as approved by the applicable IRB/EC, a relative or legally authorized representative can sign the data release form to collect additional retrospective data as documented in the subject charts. Local IRB/EC procedures must be followed here.

The refusal of a subject (as applicable relative or legally authorized representative) to sign the data release form and therefore not agreeing to the collection of additional retrospective data must never interfere with the subject-physician relationship or future subject treatment.

Should there be any change to this CIP, directly affecting the data privacy of the subject, a modification of the data release form is required. The data release form needs to be signed and personally dated by the investigator or authorized designee and the subject or relative/legally authorized representative (re-consenting if required) after approval by the sponsor and the IRB/EC.

A copy of the fully executed data release form (if required) must be provided to the subject (as applicable to the relative or legally authorized representative) and the original maintained in the trial files / subject files.

10.5. Randomization and Treatment Assignment (N/A)

Not applicable as retrospective data collection only.

Within the FIRE AND ICE Trial the subjects were randomized into two parallel trial groups, namely “Cryo” and “RF”. Randomization was stratified by an age-limit of 65 years, providing the same numbers of treatment assignments per group in both age-cohorts (≤ 65 years versus > 65 years).

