## 5. Investigation Plan

The Fire and Ice Re-Ablations study is a retrospective chart review on a subset of (at a maximum) 110 subjects from the original FIRE AND ICE randomized trial who had repeat ablation procedures during the trial. The inclusion criteria for the Fire and Ice Re-Ablations study are (1) consent for data collection as required per local law (data release form - DRF) and (2) meeting all entry criteria for the original trial at their time of enrollment in it (e.g., consent to be randomized to cryoballoon ablation or RF ablation for drug-refractory paroxysmal atrial fibrillation, able to comply with study procedure, 18 – 75 years in age, no recent cardiovascular operations, etc.).

One final analysis will be completed. At the completion of the review by the endpoint review committee (ERC), the ERC classifications will be entered into the e-capture.net database (hosted by the contract research organization genae), and the database will be frozen. Analyses comparing randomization arms will not be conducted until after the database is frozen.

The Fire and Ice Re-Ablations study design is a retrospective cohort study. It is noted that while subjects were initially randomized to receive either cryoballoon or RF catheter ablation in the original Fire and Ice trial, non-random consequences of the therapies themselves, as well as potentially non-random decisions affecting subject eligibility (e.g., whether a repeat ablation would be performed) limit the strength of inferences between groups compared to the original randomized trial.

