### Analysis methods

The first re-ablation for each subject will be used for analysis. Each first re-ablation will be grouped into the following categories:

1. atrial fibrillation (paroxysmal)
2. atrial fibrillation (persistent)
3. atrial flutter or atrial tachycardia
4. other

The percent of subjects by indication for re-ablation will be summarized in a frequency table. The distribution of type of arrhythmia will be compared between randomization arms using exact methods.

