## Analysis Methods

The first re-ablation for each subject will be used for analysis. The number of electrically isolated pulmonary veins will be assessed for each subject and the number of PVs isolated will be compared between randomization arms using a two-sample t-test. It is anticipated that the majority of subjects will have four major pulmonary veins; LIPV, LSPV, RIPV, and RSPV. If a subject has an anatomy in which electrical isolation of more or less than the four major PVs are tested, the number of electrically isolated pulmonary veins for that subject will be normalized to 4.

In addition, a logistic regression model will be fit, to test whether cryo vs RF therapy affect the odds of pulmonary vein reconnection. In the example code below, observations are successes and trials at the subject level, and SAS proc logistic (using trials events syntax) is used. This model assumes similar probabilities of reconnection for all veins within a subject (e.g., reconnection probability is not significantly different between LSPV, LIPV, RSPV, RIPV). This assumption will be tested using frequency tables and Fisher's exact test to assess whether reconnection rates are independent of treatment group by each anatomic location of ablation. This testing will only be performed for locations with 5 or more subjects treated per arm. Odds ratios and corresponding confidence intervals will be back-transformed into probabilities for presentation purposes.

```
proc logistic;
class rand (param = ref ref = 'RF') <other covariates>;
model N_reconnected/N_possible = rand <other covariates>;
run;
```

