## Analysis methods

The number and location of gaps will be presented using summary statistics. Summary statistics are, in this case, frequencies and proportions. Additionally, a contour or density plot may be presented, with higher densities indicating greater numbers of observed reconnections.

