#### Analysis methods

The first re-ablation for each subject will be used for analysis. The number of lesion sets for each subject will be counted. If a subject has multiple PVs ablated, each PV will count as a lesion set towards the subjects total count. The number of lesion sets will be compared between randomization arms using a two-sample t-test.

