## 6.4. Handling of Missing, Unused, and Spurious Data and Dropouts

[figure not shown]
It is anticipated that approximately 90% of the eligible subjects will be re-consented (DRF) and have available data from charts with which to perform an abstraction. Of these, some subjects' records will not contain data for one or more endpoints. Also, in some instances, charts from re-consenting subjects may contain complete data, but it will contain values that cannot be used in analysis of one or more objectives (i.e., when the CRF value of 'unknown' is selected instead of 'yes' or 'no'). If, for any of these reasons, 22 or more subjects do not have data for the reconnection of pulmonary veins endpoint (Objective #2) or the acute procedural success endpoint (Objective #5), further analyses relating to missingness of data may be performed.

Demographics of re-do cohorts will be compared. If no major differences in variables collected at baseline in the original Fire and Ice trial are observed between cryo and RF ablation arms, then data will be assumed "Missing Completely At Random" (MCAR) for all objectives, and only complete cases analysis will be performed. However, if differences are present and deemed significant, and <88 subjects have complete data for objectives #2 (reconnection of PV's) and #5 (acute procedural success), then up to two additional sensitivity analyses will be performed.

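### No arm comparison names the age stratum used at randomisation, the one regression model leaves its covariates open, and the planned baseline comparison triggers no adjustment

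*Protocol*

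**What the plan says.** Protocol section 10.5 states that in the parent trial "Randomization was stratified by an age-limit of 65 years", with equal allocation to the two arms in the younger (65 or below) and older (above 65) groups. It is the only stratification factor that either document names.

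The SAP's tests between the redo arms carry no stratum or covariate:

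- Objective 1: "The distribution of type of arrhythmia will be compared between randomization arms using exact methods".
- Objective 2: "the number of PVs isolated will be compared between randomization arms using a two-sample t-test".
- Objective 4: "The number of lesion sets will be compared between randomization arms using a two-sample t-test".
- Objectives 5, 8 and 9 use exact tests. Objective 6 uses three t-tests. Objective 7 uses a t-test, or a Wilcoxon test if the data are skewed.
- Objective 3 has no arm test: "The number and location of gaps will be presented using summary statistics".

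Section 6.2.2 adds a logistic model for Objective 2, with the line "model N_reconnected/N_possible = rand <other covariates>". No covariate is named anywhere in the SAP, and no rule is given for choosing one.

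Section 5 says that consequences of the therapies, and decisions such as whether to re-ablate, may be non-random and "limit the strength of inferences between groups compared to the original randomized trial". Section 6.4 says "Demographics of re-do cohorts will be compared". The result decides whether data are taken as missing completely at random and, together with the number of complete cases, whether sensitivity analyses are run. Section 6.7 plans no subgroup analyses.

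**The concern.** The arms compared here are subjects who had a re-ablation and agreed to data release. Selection into that group may differ by arm: Protocol section 4.1 reports repeat ablation in 11.8% of the cryoballoon group and 17.6% of the radiofrequency group (p=0.03). Balance on age in the full randomised set therefore does not guarantee balance on age among the redo subjects. If the arms differ in age, and age is related to an outcome, part of the observed cryo-RF difference is an age difference.

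The SAP will look at baseline differences between the redo arms, but a difference in age would change none of the arm comparisons. The one model that could take covariates leaves them to be filled in later. Since arm comparisons start only after the database freeze, nothing in the text prevents a choice made with arm results in view. At stake is modest bias in comparisons that SAP section 3 says are meant for the final report and planned publications, and some freedom in the model for the comparison that SAP section 7 singles out.

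**Working it through.** **The plan's own figure.** The only computed figure for an arm comparison is the Objective 2 power in SAP Table 1: 0.3%, 7.1%, 40.5%, 87.5% and 99.0% at differences of 0.34, 0.37, 0.40, 0.43 and 0.46 veins per subject. With 40 and 59 subjects and SD 0.93, ordinary two-sided power is 43%, 49%, 56%, 62% and 68%, so the table does not reproduce as ordinary power. That is a separate matter. Below I use only the SD and the planning rates from SAP section 7.

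**Inputs from the documents.** 110 eligible subjects; 90% consent; SD 0.93; planning reconnection rates 36.8% and 58.1%, a difference of 4 × (0.581 − 0.368) = 0.852 veins per subject.

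**Arm sizes (derived).** 378 × 0.118 = 44.6 and 384 × 0.176 = 67.6, total 112.2. Scaled to 110 this is about 44 and 66; at 90% consent, about 40 and 59.

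**Assumptions (not in the documents).** Share over 65 of about 25% to 30%; a gap between arms of 0, 10 or 20 percentage points; an age effect of 0 to 0.67 veins per subject. The upper end corresponds to an odds ratio of 2.0 per vein at a base rate of 0.5: 4 × (0.667 − 0.5) = 0.67. An odds ratio of 1.5 gives 4 × (0.6 − 0.5) = 0.40.

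**Bias of the unadjusted difference** = gap in share over 65 × age effect in veins:

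| Age effect (veins) | 10-point gap | 20-point gap |
|---|---|---|
| 0 | 0 | 0 |
| 0.25 | 0.025 | 0.05 |
| 0.40 (OR 1.5) | 0.04 | 0.08 |
| 0.50 | 0.05 | 0.10 |
| 0.67 (OR 2.0) | 0.067 | 0.133 |

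The sign depends on which arm has more older subjects. With no gap, every entry is zero.

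**How likely such gaps are by chance.** SE of the difference in shares = √[0.25 × 0.75 × (1/40 + 1/59)] = 0.089. A 10-point gap is 0.10/0.089 = 1.1 SE, which is unremarkable. A 20-point gap is 0.20/0.089 = 2.2 SE (two-sided p about 0.025), which would be unusual without selection related to age.

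**Scale.** The smallest significant difference is about 1.985 × 0.93 × √(1/40 + 1/59) = 0.38 veins. A bias of 0.025 to 0.133 is 7% to 35% of that, but 3% to 16% of the planning difference of 0.852.

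**Simulated effect of adding the age term** (linear model, arms 40/59, residual SD 0.95, 5,000 runs per scenario, so the simulation error on a 5% rate is about 0.3 points):

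| Share over 65, cryo/RF | Age effect | Bias, unadjusted | Type I error, unadjusted | Type I error, adjusted |
|---|---|---|---|---|
| 30%/30% | 0.50 | 0.00 | 5.6% | 5.8% |
| 25%/35% | 0.25 | 0.02 | 5.2% | 4.6% |
| 25%/35% | 0.50 | 0.05 | 5.4% | 4.5% |
| 20%/40% | 0.25 | 0.05 | 5.5% | 5.2% |
| 20%/40% | 0.50 | 0.10 | 7.5% | 4.6% |

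Only the last row shows a clear rise in type I error. The adjusted estimate was free of age bias throughout.

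**Cost in power** at a true difference of 0.55 veins with no age effect: 80.1% unadjusted against 79.9% adjusted with equal shares; 79.3% against 78.0% with a 10-point gap; 79.9% against 77.8% with a 20-point gap. The largest loss is about 2 points.

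**The case against.** Four arguments on the other side carry weight.

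1. The case for adjusting for a stratification factor belongs to the analysis of the randomised set. In a subset selected after randomisation, the former stratum has no special status. Age is one candidate confounder among several, and neither document says that it is related to any of these outcomes. This stands: the reason to adjust here is possible confounding, not a design requirement.
2. One binary age term leaves most of the selection that SAP section 5 describes untouched. This also stands and limits what the change can claim.
3. The size rests on assumed inputs. An age effect of 0.67 veins is 0.67/0.852, about 79% of the whole planned arm difference, and figures of 0.10 or more need a 20-point gap. This stands, so the upper end is a bound under severe assumptions and not an expectation.
4. SAP section 7 calls the objectives mainly descriptive, and section 5 already carries a caveat on inference. This lowers the stakes but does not close the point. Section 7 then names the reconnection comparison as of particular interest, section 6.2.2 asks whether therapy affects the odds of reconnection, and section 6.5 sets a 0.05 level for all tests.

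A reader might also infer two stronger things that the documents do not support. The first is that every arm comparison, including the regression, leaves age out. The Objective 2 model has an open covariate slot, so it is unspecified and not shown to omit age. The second is that the SAP admits that age balance is lost or that the redo arms are no longer randomised groups. It says only that inference is limited, and in that passage it does not discuss age balance or strata.

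**Conclusion.** The point holds as a minor gap in specification. The tests for Objectives 1, 2 and 4 to 9 are unadjusted, the Objective 2 logistic model names no covariates, and a baseline imbalance between the redo arms would alter no arm comparison. Age, already used to stratify the parent trial, is an obvious variable to fix in advance.

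The likely effect is small. Under assumed gaps of 10 to 20 points and age effects of 0.25 to 0.67 veins, the unadjusted Objective 2 difference would be biased by about 0.02 to 0.13 veins per subject, in either direction. It would not be biased at all if age is balanced or unrelated to reconnection. The documents cannot say which case applies, because they give neither the age split of the redo arms nor an age effect. Effects on the other objectives were not quantified. An age-adjusted result removes the age part of any confounding only and does not restore a randomised comparison.

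**What to change.** In the SAP:

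- **Objective 2 logistic model (section 6.2.2):** replace the open slot with age stratum (65 or below, above 65) as a fixed covariate. Since the section back-transforms results into probabilities, state whether these are given per stratum or averaged over strata.
- **Objectives 2, 4 and 6:** add linear models with arm and age stratum.
- **Objectives 5, 8 and 9:** add exact tests stratified by age group.
- **Objectives 1 and 7:** add stratified versions if all arm tests are to be covered, for example a van Elteren test where Objective 7 falls back on Wilcoxon.
- **Reporting:** keep the planned unadjusted results alongside. State that adjustment addresses age only, not the remaining selection into re-ablation or consent.
- **Section 6.4:** say whether the baseline comparison leads to any further adjustment or is descriptive only.

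The cost is SAP wording and slightly more programming. No new data should be needed: age group had to be known at randomisation, Protocol section 15.4 keeps the same identifiers so that the two data sets can be merged, and SAP section 6.4 already draws on parent-trial baseline variables. If age is unrelated to outcome, the price is at most about 2 points of power in the simulated scenarios.
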